4.1.1.4 Long-term Follow-up

All surviving participants will enter the long-term follow-up period after discontinuing from the active follow-up period except for participants who explicitly withdraw consent or are lost to follow-up.

Participants will be followed for OS and subsequent anti-cancer therapy at 3-month intervals (\pm 14 days) until the end of the study, withdrawal of consent, lost to follow-up, or death, whichever comes first (telephone contact is sufficient). Participants may be contacted at additional times throughout the course of the study in order to collect survival data to ensure that long-term follow-up data is current.

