6.5 Concomitant Therapy

Medication other than the investigational products should not be taken during the study without consulting the investigator.

Any medication that is considered necessary for the participant's welfare, and which is not expected to interfere with the evaluation of the study medications, may be given at the discretion of the investigator.

All concomitant medications that may affect efficacy or toxicity or are taken for any concurrent medical conditions at the time of enrollment or during the study (including start/stop dates, dose frequency, route of administration and indication) must be recorded in the participant's source documentation, as well as in the appropriate pages of the eCRF.

In general, participants should be closely monitored for side effects of all concomitant medications regardless of elimination pathway, especially those with narrow therapeutic index, such as warfarin, quinidine and cyclosporine.

Administration of contrast media for protocol-specified radiological procedures does not need to be reported, unless there is an AE related to the contrast medium injection (e.g. allergic reaction).

Medications or vaccinations specifically prohibited in the exclusion criteria are not allowed during the ongoing trial. If there is a clinical indication for any medication or vaccination specifically prohibited during the trial, discontinuation from trial therapy or vaccination may be required. The investigator should discuss any questions regarding this with the sponsor. The final decision on any supportive therapy or vaccination rests with the investigator and/or the participant's primary physician. However, the decision to continue the participant on study treatment requires the mutual agreement of the investigator, the sponsor and the participant.

Listed below are specific prohibited medications for concomitant therapy or vaccination during the course of the study:

- Antineoplastic systemic chemotherapy or biological therapy
- Immunotherapy not specified in this protocol
- Chemotherapy not specified in this protocol
- Investigational agents other than regorafenib and pembrolizumab
- Radiation therapy
 - Note: Palliative radiotherapy during the study for local pain control or to the brain may be allowed at the investigator's discretion.

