6.5.3 Prohibited Prior and Concomitant Therapies

Participants are prohibited from receiving the following therapies during the screening and intervention periods of this trial:

• The use of systemic corticosteroids or immunosuppressants before starting pembrolizumab should be avoided because of their potential interference with the

Page 56 of 141

pharmacodynamic activity and efficacy of pembrolizumab. Note: replacement therapy such as physiologic corticosteroid replacement therapy for adrenal or pituitary insufficiency (in dosing not exceeding 10 mg daily of prednisone equivalent) is not considered a form of systemic treatment, and inhaled steroids are allowed for management of asthma. Moreover, systemic corticosteroids or other immunosuppressants can be used after starting pembrolizumab to treat immunerelated adverse reactions.

- Disease-specific anti-neoplastic therapies, including kinase inhibitors, immunotherapy, chemotherapy, or experimental therapies other than regorafenib and pembrolizumab.
- Surgery for symptom management or tumor control.
- Strong CYP3A4 inhibitors or CYP3A4 inducers (See Section 6.5.1.1, and Appendix 6 in Section 10.6).
- Co-administration of strong UGT1A9 inhibitors (e.g. mefenamic acid, diflunisal, and niflumic acid) during regorafenib treatment should be avoided, as their influence on the steady-state exposure of regorafenib and its metabolites has not been studied.
- Live vaccines or live attenuated replication competent vaccines within 30 days prior to the first dose of trial treatment and while participating in the trial. Seasonal injectable influenza vaccines and vaccines administered in a pandemic context are allowed.

The exclusion criteria describe other medications that are prohibited in this trial (Section 5.2). Participants who, in the assessment by the investigator, require the use of any of the aforementioned treatments for clinical management should be removed from the study.

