6.7 Intervention after the End of the Study

Continued Access: Participants who are still on study intervention at the time of study completion/termination may continue to receive study intervention if they are experiencing clinical benefit. Continued access to study intervention will end when a criterion for discontinuation is met or 18 administrations of pembrolizumab had been administered. However, continuation of treatment with regorafenib can be individually discussed with the investigator for participants who do not experience disease progression after 2 years based on clinical benefit.

7. Discontinuation of Study Intervention and Participant Discontinuation / Withdrawal

All participants who enter the study should complete all applicable study periods, including the EoT visit. Participants can be withdrawn from any study period at any time.

Discontinuation from the intervention period alone does not constitute withdrawal from the study.

Participants who withdraw from the intervention period for any reason should come to the site for the safety follow-up visits and are to be encouraged to remain on the study for follow-up of primary, secondary and other objectives (i.e. continue in the active follow-up and long-term follow-up periods). Participants are expected to participate in follow-up unless they explicitly object. Withdrawal of consent to the intervention period should be documented in the participant's medical record. If the participant does not wish to be followed up further, this additional consent withdrawal for follow-up must also be documented.

For a full list of withdrawal criteria, refer to Section 7.2.

In all cases, the reason for withdrawal must be recorded in the participant's medical records and in the eCRF. For participants who withdraw consent, no further study-related procedures will be allowed. The participant will not suffer any disadvantage as a result.

Page 76 of 141

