7.1 Discontinuation of Study Intervention

In some circumstances, it may be necessary for a participant to permanently discontinue (definitive discontinuation) study intervention. If study intervention is definitively discontinued, the participant will remain in the study to be evaluated for disease progression and/or OS. See the SoA (Section 1.3.1) for data to be collected at the time of withdrawal of study intervention, in follow-up, and for any further evaluations that need to be completed.

The study interventions may be interrupted for situations other than treatment-related AEs such as medical / surgical events or logistical reasons not related to study therapy. Participants should be placed back on study therapy within 3 weeks of the scheduled interruption, unless otherwise discussed with the sponsor. The reason for interruption should be documented in the participant's study record

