7.2 Participant Discontinuation/Withdrawal from the Study

A participant must be withdrawn from the study at any time at his/her own request or at the request of their legally acceptable representative (if acceptable by local law).

A participant may be withdrawn from the study at any time at the discretion of the investigator for safety, behavioral, compliance, or administrative reasons. This is expected to be uncommon.

If the participant withdraws consent for disclosure of future information, the sponsor may retain and continue to use any data collected before such a withdrawal of consent.

If a participant withdraws from the study, and additionally requests destruction of her/his samples taken but not yet tested, the investigator must document this (either destruction by site or request to central lab, as applicable) in the site study records.

Withdrawal from active follow-up

Participants MUST be withdrawn from active follow-up if any of the following occurs:

- At their own request or at the request of their legally acceptable representative (if acceptable by local law). At any time during the study and without giving reasons, a participant may decline to participate further. The participant will not suffer any disadvantage as a result.
- Radiologically confirmed PD is observed and/or clinical progression (for participants who discontinued study intervention before PD due to any other reason).
- Start of subsequent systemic anti-cancer treatment.
- Development of a second primary malignancy that requires a different treatment.
- Substantial non-compliance with the requirements of the study.
- If, in the investigator's opinion, continuation of the active visits would be harmful to the participant's well-being.
- Participants lost to follow-up.
- Death.

Participants MAY be withdrawn from active follow-up if any of the following occurs:

• At the specific request of the sponsor and in liaison with the investigator (e.g. obvious non-compliance).

Withdrawal from long-term follow-up

Participants MUST be withdrawn from long-term follow-up if any of the following occurs:

• Withdrawal of consent to long-term follow-up.

Page 79 of 141

- Participants lost to follow-up.
- Death.

Participants MAY be withdrawn from long-term follow-up if any of the following occurs:

• At the specific request of the sponsor and in liaison with the investigator (e.g. obvious non-compliance).

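### Section 6.5.3 removes from the study participants who need a prohibited treatment, whereas Sections 7 and 7.1 end only their study treatment; the text should say that follow-up continues

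*Protocol*

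**What the plan says.** Protocol Section 6.5.3 lists therapies prohibited in the screening and intervention periods: other anti-neoplastic therapy, surgery for symptoms or tumor control, strong CYP3A4 inhibitors and CYP3A4 inducers, strong UGT1A9 inhibitors, live vaccines, and steroids or immunosuppressants before pembrolizumab starts. It adds the medications barred by the exclusion criteria. Its closing rule is that participants who, in the investigator's assessment, "require the use of any of the aforementioned treatments for clinical management should be removed from the study".

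Other sections bear on the same event:

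- Section 6.5, on a prohibited medication that becomes clinically indicated: "discontinuation from trial therapy or vaccination may be required". It leaves room to stay on treatment, since "the decision to continue the participant on study treatment requires the mutual agreement of the investigator, the sponsor and the participant". It says nothing about follow-up.
- Section 7, opening text: "Discontinuation from the intervention period alone does not constitute withdrawal from the study".
- Section 7.1: "If study intervention is definitively discontinued, the participant will remain in the study to be evaluated for disease progression and/or OS".
- Section 4.1.1.3 follows for progression those who discontinue for reasons other than PD, death, withdrawn consent or loss to follow-up.
- Section 4.1.1.4: "All surviving participants will enter the long-term follow-up period after discontinuing from the active follow-up period", with exceptions only for explicit withdrawal of consent and loss to follow-up.
- Section 7.2 lets the investigator withdraw a participant from the study "at the discretion of the investigator for safety, behavioral, compliance, or administrative reasons" and expects this to be uncommon. Need for a prohibited treatment is not named.

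**The concern.** Section 7 is built on the difference between leaving treatment and leaving the study. Section 6.5.3 uses the more drastic term, as a general rule, for an event that the other sections treat as at most the end of study treatment. Two sites could each follow the protocol and handle the same participant differently: one stops scans and survival calls, the other continues them.

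At stake are the time-to-event endpoints. Protocol Section 9.4.1.3 censors DOR at the last tumor evaluation, and SAP Section 5.5.2 summarises PFS and OS by Kaplan-Meier with rates at 6, 12, 18 and 24 months. If follow-up ends because a participant needed surgery, an interacting drug or another cancer therapy, the censoring may be related to prognosis. SAP v3.0 plans no sensitivity analysis for the primary or secondary endpoints (Sections 5.3.3 and 5.4.1.3).

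**Working it through.** **Who is exposed.** Setting the sections side by side by type of case:

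1. *Not yet dosed.* Someone in screening who needs a prohibited treatment and never starts is a screen failure (Section 5.4) and is outside the Full Analysis Set. There is no conflict.
2. *Progressed and off study treatment.* Section 6.5.5 prohibits nothing during active and long-term follow-up, so next-line therapy does not trigger 6.5.3.
3. *On treatment, starts other systemic anti-cancer therapy.* Section 7.1.1.1 ends study intervention and Section 7.2 ends active follow-up, so scans stop on either reading. A literal 6.5.3 additionally loses survival and subsequent-therapy data.
4. *On treatment, needs an interacting drug, live vaccine or listed surgery.* A literal 6.5.3 loses later scans and survival contact. Sections 4.1.1.3, 4.1.1.4 and 7.1 keep both.

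Only cases 3 and 4 matter. The documents give no rate for either.

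**OS, illustration on assumed values.** Assume exponential time to progression with median 4 months (a = ln 2/4), exponential survival after progression with median 6 months (b = ln 2/6), no death before progression, and a fraction f of all participants censored at progression. With P0 = exp(−at) and P1 = a/(b−a) × [exp(−at) − exp(−bt)], the Kaplan-Meier curve tends to S(t) = exp{−∫ b(1−f)P1/[P0 + (1−f)P1] du}. Its median is:

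- f = 0: 12.0 months
- f = 1%: 12.0
- f = 3%: 12.1
- f = 10%: 12.4
- f = 20%: 12.8
- f = 40%: 13.9

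With a progression median of 3 months, the values for f = 0, 10%, 20% and 40% are 10.6, 10.9, 11.2 and 12.1. The model censors at progression, which is where case 2 shows 6.5.3 seldom applies, so the larger fractions are not realistic estimates.

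**ORR.** The plan's own figures (protocol Section 9.2) come first, and they reproduce:

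- 27 of 93 at a 20% null: exact one-sided alpha 0.0238 (26 gives 0.0408).
- 34 of 119: alpha 0.0158 (33 gives 0.0264).
- Conditional power at 35%, scenario 1: Σ over x = 8 to 26 of P(X1 = x) × P(X2 ≥ 27 − x), divided by P(X1 ≥ 8), with X1 ~ Bin(26, 0.35) and X2 ~ Bin(67, 0.35). This is 0.7070/0.7404 = 95.5%.
- Scenario 2, the same with two cohorts of 26 and a boundary of 34: 0.5425/0.5481 = 99.0%.

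Both meet the stated 95%. Now suppose a share f of would-be responders is removed before the confirmation scan, which Section 8.1 places at least 4 weeks after the first response, and is scored as non-responding. Then p = 0.35 × (1 − f):

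- f = 2% (p = 34.3%): scenario 1 94.1%, scenario 2 98.5%
- f = 5% (p = 33.3%): 91.5% and 97.6%
- f = 10% (p = 31.5%): 85.3% and 94.9%

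For scale, 93 × 0.35 = 32.6 expected responders, so f = 5% is 1.6 people. One responder is 1/26 = 3.8 percentage points of a pilot cohort and 1/93 = 1.1 points of the final sample. These figures show only how sensitive the design would be. Section 10.5.1 counts best overall response only up to the end of intervention, so for a participant whose treatment stops, a later confirming scan may not count even if follow-up continues.

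**The case against.** The best case on the other side is that this is loose wording with little consequence.

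- Section 4.1.1.3 itself speaks of people who discontinue from the study and then follows them for progression. Section 4.1.1.4 admits all survivors to long-term follow-up with two exceptions. No section says that removal under 6.5.3 stops scans or calls. This stands: loss of data is a risk under a literal reading, not something the protocol prescribes.
- The rule covers only screening and treatment, and Section 6.5.5 frees participants afterwards. This also stands, and it takes out most participants who progress.
- Section 7.2 could absorb individual cases under safety or compliance. That is true case by case, but 7.2 is permissive and expects few such withdrawals, whereas 6.5.3 states a general rule.
- OS and PFS are exploratory (protocol Table 3–1) and SAP Section 5.4.1.2 only lists DOR. Recruitment stopped early (SAP version history) and SAP Section 5.8 plans no interim analysis, so the pilot criterion has little current weight. This lowers the stakes without removing the contradiction.

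A reader might infer that outcome data are in fact lost selectively and that OS is overestimated. The documents do not support that: they give no rate, and the OS shifts above rest on assumed medians and fractions. A reader might also infer that Section 6.5 itself requires follow-up. It concerns only trial therapy; Sections 7, 7.1, 4.1.1.3 and 4.1.1.4 carry the follow-up requirement.

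**Conclusion.** The contradiction is real and is in the current text. Read literally, 6.5.3 ends participation where Sections 7 and 7.1 end only treatment. The consequence is a risk, of unknown and probably small size, of avoidable and possibly informative censoring of DOR, PFS and OS among participants still on treatment. Under the illustration, 1 to 3% removed moves a 12.0-month OS median by no more than about 0.1 month.

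It would be tempting to conclude that the primary analysis loses power. The documents do not support that. The Full Analysis Set denominator is unchanged (protocol Sections 9.3 and 9.4.1.2), a response confirmed before removal still counts, and post-treatment confirmation may not count in any case. The remaining route is a participant with an unconfirmed first response who would have stayed on treatment under Section 6.5. Any error there lowers ORR.

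The main analytical approach for ORR is deferred to SAP v2.0, which was not available, so further censoring or response rules could not be checked.

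**What to change.** Amend the last sentence of Section 6.5.3 so that it does not end study participation. State that treated participants remain in safety follow-up, in tumor assessment until PD or new anti-cancer therapy, and in long-term survival follow-up, unless they withdraw consent. Align the wording with Sections 4.1.1.3, 4.1.1.4, 7 and 7.2.

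Separately, Sections 6.5, 6.5.3 and 7.1 must be reconciled by the sponsor on what happens to study treatment when a prohibited therapy is needed. This review does not say which rule is right.

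The follow-up change costs one sentence in an amendment and a note to sites. It adds no visits, because the follow-up is already in the Schedule of Activities. Since recruitment has stopped, it would also help to identify, in the discontinuation reasons already tabulated under SAP Section 5.2, any participant whose follow-up ended on this ground. That would replace the assumed fractions with a count.

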6.5.4 Permitted Concomitant Therapies

All concomitant medications (including start / stop dates, total daily dose, and indication) must be recorded in the participant's source documentation and in the eCRF.

- Treatment with non-conventional therapies (e.g. herbs or acupuncture) and vitamin/mineral supplements is acceptable provided that they do not interfere with the study endpoints, in the opinion of the investigator. However, St John's Wort (herbal preparation based on the plant species hypericum) is not permitted.
- Participants who are therapeutically treated with an agent such as warfarin or heparin or novel oral anticoagulants (NOACs) such as dabigatran or rivaroxaban will be allowed to participate provided that no prior evidence of underlying abnormality in coagulation parameters exists. Close monitoring of at least weekly evaluations for participants on warfarin will be performed until the INR is stable based on a measurement that is pre-dose as defined by the local standard of care.
- P-glycoprotein substrates: clinical data indicate that regorafenib has no effect on digoxin pharmacokinetics, therefore can be given concomitantly with p-glycoprotein substrates, such as digoxin, without a clinically meaningful drug interaction (see Section 6.5.1.3).
- Participants may receive palliative or supportive care for any underlying illness.
- Palliative and supportive care for other disease-related symptoms and for toxicity associated with treatment will be offered to all participants on this trial. The use of anti-diarrheal or anti-emetics according to standard practice is strongly encouraged.

- Bisphosphonates and/or RANKL (receptor activator of nuclear factor kappa-B ligand) inhibitor therapies (such as denosumab) for bone metastases may be continued if treatment with an agent from one of these two classes was initiated prior to signing informed consent. Bisphosphonates and/or RANKL inhibitor therapies cannot be initiated after informed consent has been signed, unless in the opinion of the investigator, the participant does not have PD.
- Radiotherapy:
 - o Palliative radiotherapy during the study is allowed for local pain control after individual benefit-risk assessment provided that:
 - In the opinion of the investigator, the participant does not have PD,
 - No more than 25% of the participant's bone marrow is irradiated,
 - The radiation field does not encompass a target lesion, and
 - The radiation field does not encompass a lung field (to reduce the risk for interstitial lung disease [ILD] caused by irradiation pneumonitis).
 - Regorafenib may only be continued during palliative radiotherapy after an individual benefit-risk assessment. The investigator should consult the sponsor.
 - o Pembrolizumab must be held during radiation treatment and should be resumed no earlier than the next scheduled administration of study intervention.

Note: administration of palliative radiation therapy to a symptomatic solitary lesion or to the brain will be considered clinical progression for the purposes of determining PFS.

- Analgesics.
- Nutritional support.
- Major surgery for any reason different than symptom management or tumor control should only be performed during the study period if, in the opinion of the investigator and after careful individual benefit / risk assessment (taking into account the potential wound healing complications that have been described with all anti-VEGF drugs), the surgery will be beneficial for the participant. It is recommended to stop regorafenib treatment two weeks before surgery. The decision to resume regorafenib after surgery should be based on clinical judgment of adequate wound healing. Participants should be placed back on study therapy within 4 weeks of the scheduled interruption of regorafenib.

Note: if treatment interruption of regorafenib will be >28 consecutive days - including the 1 week drug holiday – the participant must be discontinued from regorafenib. However, continuation of regorafenib may be considered if, in the investigator's opinion, the participant may continue to benefit from the regorafenib treatment, and after consultation with the sponsor.

Participants who experience a delay of more than 12 weeks before the subsequent pembrolizumab infusion must be discontinued from pembrolizumab.

• Participants may receive other medications that the investigator deems to be medically necessary.

Page 58 of 141

